3.1. STUDY OUTCOME MEASURES

The primary outcome measure is the diameter variation ranges of the left CIV in adults referred to the vascular ultrasound department.

The secondary outcome measure is the inter- and intra-operator variation of the diameter measurement of the left CIV using duplex ultrasound, in adult patients referred to the vascular ultrasound department.

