1.2. RATIONALE FOR CURRENT STUDY

More widespread use of ultrasound for examining the iliac veins would be beneficial as it may avoid the need to expose patients to the invasive procedures requiring radiation and contrast agents that are necessary for venography and IVUS. Previous studies examining duplex ultrasound and iliac veins, as mentioned above, have examined the use of velocity ratios, interrogation of the CFV and examination of phasicity but have not investigated using ultrasound to measure the absolute diameter of the CIV. There is currently no definitive diameter that the CIV can be considered compressed or not compressed. All of the previous studies used symptomatic patients only and so it cannot be assumed that the results would correlate in asymptomatic patients. Also, it is known that ultrasound is highly operator dependent but none of the previous studies examined the impact of this on measuring the CIV diameter. Therefore, further work needs to be carried out to assess the use of ultrasound for imaging the left CIV and aiding MTS diagnosis.

The principle research question is whether duplex ultrasound could be used to image the left CIV and investigate diameter ranges that can help in the diagnosis of MTS. The first objective is to use duplex ultrasound to image the left CIV in a cohort of patients referred to the vascular ultrasound clinic. The second objective is to determine inter- and intra-observer variation of the diameter measurement of the left CIV using duplex ultrasound. The hypothesis is that ultrasound can be used to image left CIV compression and the measurements obtained during the examination are highly reproducible both within an operator and between operators.

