If the results of this research study find that ultrasound can be used to image the left CIV, can define 'normal' diameter ranges and is a reproducible diagnostic tool, then this could reduce the time taken for patients presenting with symptoms of MTS to be diagnosed. Ultrasound is a quick and readily available imaging tool, and so creating an appropriate scanning protocol will enable regular scanning and screening of patients who may have this condition. As well as aiding diagnosis it should also help reduce the number of patients with this condition that go on to suffer from further severe complications such as DVT. These results should also help identify which patients need to go on to have the more invasive tests and rule out patients that do not require them. Iliac vein scanning with ultrasound is not routinely performed in all vascular departments across the country, with many only taking indirect measurements from the CFV's. If a benefit is found to doing this scan then it could be introduced to many more/all departments, benefiting many more patients.

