2. STUDY OBJECTIVES

The primary objective of this study is to investigate diameter variation of the left CIV based on posture in adults referred to the vascular ultrasound department, using duplex ultrasound.

The secondary objective of this study is to determine inter- and intra-observer variation of the diameter measurement of the left CIV using duplex ultrasound, in adults referred to the vascular ultrasound department.

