- A clinical vascular scientist will perform the study ultrasound scan and take three readings of the left CIV with the patient lying flat and three readings of the left CIV with the patient at a 45 degree angle on a tilted examination couch - 10 minutes
- Two further clinical vascular scientists will perform the same study scan and take the same readings - 20 minutes
- Patient will be thanked for their time and a routine follow up appointment will be made with the referring clinician.

The below flow chart illustrates this order of procedures:

Prior to the ultrasound scan appointment:

During the ultrasound scan appointment:

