7. STATISTICS AND DATA ANALYSIS

The sample size has been calculated using a sample size calculator assuming a prevalence of 2%, confidence level of 95% and margin of error of 5%. This calculation gives a sample size of 31. This sample size is in line with a previous study by Mousa et al. (2016) which had a sample size of 36.

A one-way ancova test will be performed to assess the difference in iliac vein diameter between the two groups. An intraclass correlation coefficient will be used to measure intra- and inter-observer reliability. Support will be provided from the Imperial Statistics Services during the analysis phase.

Statistics and data analysis aspects of the study have been reviewed by [name], the academic supervisor at Manchester Metropolitan University.

Data and all appropriate documentation will be stored for a minimum of 10 years after the completion of the study, including the follow-up period.

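### The primary outcome is a range of left CIV diameter and the primary objective is variation by posture, but the two analyses in Section 7 estimate neither

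*Combined protocol and SAP*

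**What the plan says.** Section 3.1 defines the outcome: "The primary outcome measure is the diameter variation ranges of the left CIV in adults referred to the vascular ultrasound department". It names no percentile, limit or other statistic. Section 2 puts the aim in terms of position: "The primary objective of this study is to investigate diameter variation of the left CIV based on posture in adults". Section 1.2 gives the purpose, which is to "investigate diameter ranges that can help in the diagnosis of MTS", and looks ahead to a result that "can define 'normal' diameter ranges and is a reproducible diagnostic tool".

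Section 7 lists two analyses. The first is: "A one-way ancova test will be performed to assess the difference in iliac vein diameter between the two groups". The second is: "An intraclass correlation coefficient will be used to measure intra- and inter-observer reliability". The ANCOVA covariate is not named.

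On data collection, Section 3 has one vascular scientist "take three readings of the left CIV with the patient lying flat and three readings of the left CIV with the patient at a 45" (the last figure is the tilt of the couch in degrees). The next step reads: "Two further clinical vascular scientists will perform the same study scan and take the same readings". Recruitment is 40 patients, 20 symptomatic and 20 asymptomatic for lower limb venous disease.

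**The concern.** Followed exactly, Section 7 yields an adjusted difference between two group means and one or more reliability coefficients. It yields no diameter limits and no estimate of how diameter changes between lying flat and the tilted position. The study could finish with its declared primary outcome unreported, or reported by a method chosen after the data are seen.

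That choice matters because each patient contributes many readings. A range taken over individual readings contains measurement error as well as real differences between patients, and a range taken over patient averages contains much less. The plan does not say which is meant. A range quoted without a confidence interval would also hide how little 20 patients per group can say about the tails of a distribution, and the tails are what a normal range describes.

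**Working it through.** **Inputs from the documents.** 20 patients per group, 40 in all (Section 3). 3 scientists × 3 readings = 9 readings per posture, so 18 per patient over two postures (Section 3). Prevalence 2%, confidence 95%, margin 5%, stated n = 31 (Section 7). No diameter SD and no ICC is given, so results below are in units of the between-patient SD and the ICC is varied as an assumption.

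**1. The plan's own figure.** n = z²p(1−p)/d² = 1.96² × 0.02 × 0.98 / 0.05² = 30.12, rounded up to 31. The figure reproduces. It is the size needed to estimate a 2% prevalence to within 5 points, and it says nothing about the precision of a diameter limit.

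**2. Outcome against analysis.**

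| Reading of the primary outcome | Quantity needed | ANCOVA gives | ICC gives |
|---|---|---|---|
| Spread of diameter across patients | Lower and upper limits in units of length | Adjusted difference in group means | Ratio of variances, no units |
| Change of diameter with posture | Within-patient difference, flat minus 45 degrees | The same group contrast; no posture term is named | Agreement among readings |

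Neither row is met by either analysis.

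**3. What the missing summary rule could do.** Simulation with 10,000 replicates, normal data, between-patient SD 1 and error variance (1 − ICC)/ICC. The error is either independent for every reading, or half of it is shared by the three readings of one operator on one patient. The entries are the expected minimum-to-maximum divided by that of the error-free diameters, for 20 patients and one posture.

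| Assumed single-reading ICC | All 9 readings pooled | One reading per patient | Mean of 9 per patient |
|---|---|---|---|
| 0.50 | 1.94-1.98 | 1.41 | 1.06-1.11 |
| 0.75 | 1.49-1.53 | 1.16 | 1.02-1.04 |
| 0.90 | 1.27-1.29 | 1.05 | 1.01 |
| 0.95 | 1.18-1.19 | 1.03 | 1.00-1.01 |

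A check on the last column by formula, with independent error: √(1 + (1 − ICC)/(9 × ICC)). At ICC 0.5 this is √(1 + 1/9) = 1.054, and at 0.90 it is √(1 + 0.0123) = 1.006. Both agree with the simulation.

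Even without measurement error, a minimum-to-maximum grows with the number of patients: its expected value is 3.73 SD with 20 and 4.31 SD with 40.

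**4. Precision of a limit.** For mean ± 1.96 SD under normality, SE = SD × √(1/n + 1.96²/(2(n − 1))).

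- n = 20: √(0.0500 + 3.8416/38) = √0.1511 = 0.389; × 1.96 = ±0.76 SD.
- n = 40: √(0.0250 + 3.8416/78) = √0.0743 = 0.272; × 1.96 = ±0.53 SD.

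With 20 patients, the interval around one limit spans 2 × 0.762 = 1.52 SD, against 3.92 SD for the whole reference interval, or 39% of it.

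**5. A mean difference is not a range.** As an illustration only, 20 per group gives 80% power in an unadjusted two-sided 5% t-test for a difference of 0.91 SD. Two normal distributions of equal SD that far apart overlap by 2Φ(−0.4546) = 0.65. A significant result can therefore coexist with groups that mostly overlap.

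**The case against.** This is a feasibility study, and simple description may have been taken for granted. The Study Summary describes the outcome merely as the diameter measurement, which a comparison of diameters does address. The variance components behind an ICC, or the ANCOVA residual SD, could also be turned into limits. Part of this stands: the data and most of the modelling are already in hand. But the plan does not say that limits will be derived, and Sections 2 and 3.1 ask for variation by posture and for ranges. A pilot need not be powered, but it should analyse the outcome that it calls primary.

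One might suppose that posture enters as the unnamed covariate. Even then the stated target is the difference between the groups, not the change within a patient.

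A reader might infer that the sponsor intends to report a raw minimum-to-maximum over all readings. No section says so. The inflation in step 3 shows what an undefined summary permits. It is not a fault in a planned analysis, and it nearly disappears if readings are averaged. Section 1.2 also hypothesises high reproducibility, which points to the lower rows of that table.

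A reader might also infer that a significant ANCOVA will be used to declare a diagnostic cut-off. The documents do not support that: the language in Section 1.2 is conditional and no cut-off is planned. Nor would a measure of how well diameter separates the two groups give diagnostic accuracy for MTS. The groups are defined by lower limb venous disease, and the study procedures include no venography or IVUS reference.

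**Conclusion.** The point holds. Section 7 answers a different question from the one in Sections 2 and 3.1, and this follows from the text without any assumption. It is more than a missing detail, because the plan carried out in full still leaves the primary outcome without a result.

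The possible size of the error from the missing summary rule is conditional. It is substantial only if readings are pooled and a raw range is quoted, and small if they are averaged per patient. Those figures, and the ±0.76 SD and ±0.53 SD for the limits, assume normality; the inflation figures also rest on assumed ICCs, since the documents give none. It cannot be concluded that the sponsor's range will be wrong by any particular amount. This is a cheap improvement on data already being collected.

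**What to change.** Add to Section 7, as the analysis of the primary outcome:

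- Form one mean diameter per patient per posture from the nine readings.
- For each group and posture, report the mean, the between-patient SD and the 2.5% and 97.5% limits, each with a 95% confidence interval.
- Report the paired within-patient difference, flat minus 45 degrees, with its mean, SD, limits and 95% confidence intervals.
- From the variance components behind the ICC, report the wider range to expect for a single reading by a single operator.
- State that the limits are exploratory, quote the expected precision from step 4, and say that a significant difference in means does not by itself support a diagnostic range.

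Align the wording of Section 3.1 with Section 2, so that it is clear whether the outcome is spread across patients, change with posture, or both.

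The cost is a paragraph and one extra table, with no further patients or scans. The reported ranges will look less precise.

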4. PARTICIPANT ENTRY

4.1. PRE-REGISTRATION EVALUATIONS

Patients notes, GP referrals and current scan request forms will be examined to determine that the patient does require a vascular ultrasound scan.

4.2. INCLUSION CRITERIA

Patients will only be included if:

- They have the capacity to consent.
- They are required to have a vascular ultrasound scan in the vascular ultrasound department at ICHT.

THEY ARE 18 YEARS OF AGE OR OLDER AT THE START OF THE STUDY.

4.3. EXCLUSION CRITERIA

Patients will be excluded if:

- They do not have capacity to consent.
- They do not require a vascular ultrasound scan as part of their routine care.
- They are under 18 years of age at the start of the study.
- They are pregnant.
- They have had previous interventions/treatment for iliac vein disease.
- They have had a previous diagnosis of iliac vein thrombus.

4.4. WITHDRAWAL CRITERIA

A participant may withdraw at any time by notifying the researcher in person or in written form. If a patient withdraws from the study, any data collected up until that time will remain on file and will be included in the final study analysis.

5. ADVERSE EVENTS

5.1. DEFINITIONS

Adverse Event (AE): any untoward medical occurrence in a patient or clinical study subject.

Serious Adverse Event (SAE): any untoward medical occurrence or effect that:

- **Results in death**
- **Is life-threatening** – refers to an event in which the subject was at risk of death at the time of the event; it does not refer to an event which hypothetically might have caused death if it were more severe

- Requires hospitalisation, or prolongation of existing inpatients' hospitalisation
- Results in persistent or significant disability or incapacity
- Is a congenital anomaly or birth defect

Medical judgement should be exercised in deciding whether an AE is serious in other situations. Important AEs that are not immediately life-threatening or do not result in death or hospitalisation but may jeopardise the subject or may require intervention to prevent one of the other outcomes listed in the definition above, should also be considered serious.

5.2. REPORTING PROCEDURES

All adverse events should be reported. Depending on the nature of the event the reporting procedures below should be followed. Any questions concerning adverse event reporting should be directed to the Chief Investigator in the first instance.

5.3.1 Non serious AEs

All such events, whether expected or not, should be recorded

5.3.2 Serious AEs

An SAE form should be completed and emailed to the Chief Investigator within 24 hours. However, relapse and death due to a pre-existing, non-vascular related condition, and hospitalisations for elective treatment of a pre-existing condition do not need reporting as SAEs.

All SAEs should be reported to the London – Riverside Research Ethics Committee where in the opinion of the Chief Investigator, the event was:

- 'related', ie resulted from the administration of any of the research procedures; and
- 'unexpected', ie an event that is not listed in the protocol as an expected occurrence

Reports of related and unexpected SAEs should be submitted within 15 days of the Chief Investigator becoming aware of the event, using the NRES SAE form for non-IMP studies. The Chief Investigator must also notify the Sponsor of all related and unexpected SAEs.

Local investigators should report any SAEs as required by their Local Research Ethics Committee, Sponsor and/or Research & Development Office.

Contact details for reporting SAEs

[contact]

CI email [contact] (and contact details below)

Fax: N/A, attention N/A

Please send SAE forms to: [name]

[contact] (Mon to Fri 09.00 – 17.00)

6. ASSESSMENT AND FOLLOW-UP

This study is in addition to any NHS treatment the participants may be having, so there will be no assessment or follow-up required. In the event of discovering an

incidental finding, the participants' referring clinician will be informed via a telephone call or email from the researcher (dependant on urgency of findings e.g. the referring clinician or on-call vascular registrar will immediately be called if there is an incidental finding of acute thrombus in the iliac veins). The study will end when the last participant recruited on to the study has attended their ultrasound scan appointment.

7. STATISTICS AND DATA ANALYSIS

The sample size has been calculated using a sample size calculator assuming a prevalence of 2%, confidence level of 95% and margin of error of 5%. This calculation gives a sample size of 31. This sample size is in line with a previous study by Mousa et al. (2016) which had a sample size of 36.

A one-way ancova test will be performed to assess the difference in iliac vein diameter between the two groups. An intraclass correlation coefficient will be used to measure intra- and inter-observer reliability. Support will be provided from the Imperial Statistics Services during the analysis phase.

Statistics and data analysis aspects of the study have been reviewed by [name], the academic supervisor at Manchester Metropolitan University.

Data and all appropriate documentation will be stored for a minimum of 10 years after the completion of the study, including the follow-up period.

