8.5. SPONSOR	14
8.6. FUNDING	14
8.7. AUDITS	15
9. STUDY MANAGEMENT	15
10. PUBLICATION POLICY	15
11. REFERENCES	15

GLOSSARY OF ABBREVIATIONS

CIV	Common iliac vein
MTS	May Thurner Syndrome
DVT	Deep vein thrombosis
IVUS	Intravascular Ultrasound
CFV	Common femoral vein

KEYWORDS

Common Iliac Vein (CIV) May-Thurner Syndrome (MTS) Duplex Ultrasound

STUDY SUMMARY

TITLE The use and reproducibility of duplex ultrasound to provide indices of left Common Iliac Vein (CIV) diameter, for improved diagnosis of May Thurner Syndrome (MTS) in patients presenting with unexplained left leg swelling.

DESIGN Feasibility/Pilot Study.

AIMS To investigate the use and reproducibility of duplex ultrasound to determine diameter indices of left CIV compression.

OUTCOME MEASURES The diameter measurement of the left CIV in adults, and the inter- and intra-operator variation of the diameter measurement of the left CIV using duplex ultrasound.

POPULATION Adult patients referred to the vascular ultrasound department.

ELIGIBILITY Patients with or without venous disease, who have not had previous treatment for iliac vein disease.

DURATION 9 months

REFERENCE DIAGRAM

[if appropriate]

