3. STUDY DESIGN

The study will be a feasibility/pilot study lasting approximately six months, recruiting 40 patients from the vascular ultrasound department at Imperial College Healthcare NHS Trust. 20 patients will be symptomatic for lower limb venous disease and 20 patients will be asymptomatic. The following outlines the timeline of events for the patients recruited onto the study.

OUTPATIENT APPOINTMENT

At their outpatient appointment patients who may be eligible to take part in the study will be identified and approached. Patient notes and GP referral letters will be read prior to seeing the patient in the outpatient appointment, to identify suitable participants. Suitable participants will be those that will be requiring a vascular ultrasound scan in the vascular ultrasound department. The study will be explained and if the patient gives verbal consent to receiving study information material, then this will be given to the patient for consideration. They will be told that formal consent will be taken at their scan appointment if they agree to partake in the study and that if they choose not to partake this will not affect their usual clinical care. Participants will be given up to six weeks to decide if they would like to take part.

TELEPHONE CALL

Patients will be contacted two weeks after their outpatient appointment to enquire as to whether they would like to take part in the study. Those that decline will have their scan request form passed on to the department receptionist for booking in the usual way. Those that would like to take part in the study will have a date and time arranged to come to the department to have their scan as part of the study, followed by the scan requested by the clinical team. The study scan and the routine scan will be made on the same day to avoid the patient having to come to the hospital multiple times. Some patients from the symptomatic group may have been referred for this type of scan.

[figure not shown]
ULTRASOUND SCAN APPOINTMENT

Order of events at the scan appointment will be as follows;

[figure not shown]
- Eligibility check and formal consent - 5 minutes
- Recording of demographic details and medical history - 5 minutes
- The patient will have their routine scan performed as requested by the referring clinician - Between 30 and 90 minutes, dependent on the scan type requested.

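### Section 7 sizes the study by the margin of error for a 2% prevalence, a quantity that the study never estimates, so the stated precision applies to none of its planned results

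*Combined protocol and SAP*

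**What the plan says.** The sample-size text in Section 7 reads: "The sample size has been calculated using a sample size calculator assuming a prevalence of 2%, confidence level of 95% and margin of error"; the margin is set at 5%. It continues: "This calculation gives a sample size of 31". It does not say what condition or population the 2% refers to. The only other support is that an earlier study had a similar size, 36 patients.

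The rest of the plan is about other quantities:

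- Section 2: "The primary objective of this study is to investigate diameter variation of the left CIV based on posture in adults referred" to the department. The secondary objective is variation within and between observers.
- Section 3.1 names diameter variation ranges as the primary outcome and operator variation as the secondary outcome.
- Section 7, analysis: "A one-way ancova test will be performed to assess the difference in iliac vein diameter between the two groups", and "An intraclass correlation coefficient will be used to measure intra- and inter-observer reliability".
- Section 3, size: "The study will be a feasibility/pilot study lasting approximately six months, recruiting 40 patients from the vascular ultrasound department", of whom "20 patients will be symptomatic for lower limb venous disease and 20 patients will be asymptomatic".
- Section 3, measurements: three vascular scientists each take three readings flat and three at 45 degrees.

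**The concern.** A margin of error for a prevalence describes the precision of a percentage. It carries over neither to a mean difference in a continuous diameter, which depends on the diameter's SD, nor to an ICC, which depends on the true ICC and on the numbers of patients and operators or readings.

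The 95% confidence and 5% margin are the only precision that the protocol states. A reader could take them as the accuracy of the study's results, when they belong to a quantity that will not be reported. Section 1.2 hypothesises that the measurements reproduce very well within and between operators, yet nothing in Section 7 tells the reader how firmly 40 patients could show this, or how precisely they could show a posture change or a group difference.

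**Working it through.** **Inputs from the documents.** Prevalence 2%, confidence 95%, margin 5 points, resulting n = 31 (Section 7). Recruitment 40, as 20+20; three operators; three readings per operator and posture (Section 3). The documents give no diameter SD and no target ICC, so differences below are in SD units and the ICC values are assumptions.

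**1. The plan's own figure.** n = z²p(1−p)/d² = 1.96² × 0.02 × 0.98 / 0.05² = 30.12, rounded up to 31. It reproduces exactly.

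**2. Is a prevalence estimated anywhere?** Sections 2 and 3.1 and the analysis text of Section 7 contain none. The only similar figure is in Section 1.1, where 2-3% of lower limb DVTs are attributed to May-Thurner syndrome. That is a share of DVTs, not a prevalence in the patients recruited here.

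**3. Does the earlier study of 36 fill the gap?** As Section 1.1 describes it, that study asked whether reflux in the common femoral vein indicates iliac stenosis above 50% on IVUS. Section 7 takes no SD, effect size, ICC or precision from it.

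**4. Precision for the actual outcomes.** Given for 40 evaluable patients, and for the protocol's own 31 (16+15) in case some veins cannot be imaged.

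*Mean posture change (paired).* Half-width = t(0.975, n−1)/√n, in SDs of the within-patient change:
- n = 40: 2.023/√40 = 0.32
- n = 31: 2.042/√31 = 0.37

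*Group difference, before any covariate gain.* Half-width = t(0.975, n₁+n₂−2) × √(1/n₁+1/n₂), in SDs of diameter. The difference detectable with 80% power at two-sided 5% comes from the noncentral t distribution:
- 20+20: 2.024 × 0.3162 = 0.64; 80% power at about 0.91
- 16+15: 2.045 × 0.3594 = 0.74; 80% power at about 1.04

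*ICC, one-way F-based 95% interval.* With k = 3, F = (1+2ρ)/(1−ρ). The lower limit is (F/a−1)/(F/a+2), with a = F(0.975; n−1, 2n). The upper limit is (F×b−1)/(F×b+2), with b = F(0.975; 2n, n−1). For n = 40, a = 1.685 and b = 1.775; for n = 31, a = 1.807 and b = 1.935. Example at ρ = 0.80, n = 40: F = 2.6/0.2 = 13, F/a = 7.716, lower limit 6.716/9.716 = 0.69; F×b = 23.08, upper limit 22.08/25.08 = 0.88.

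| Assumed ICC | n = 40 | n = 31 |
|---|---|---|
| 0.70 | 0.56-0.81 | 0.53-0.83 |
| 0.80 | 0.69-0.88 | 0.67-0.89 |
| 0.90 | 0.84-0.94 | 0.83-0.95 |

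The same formula serves three operators (inter-observer, no systematic operator difference) and three readings by one operator in one posture (intra-observer).

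**5. Sensitivity to operator differences.** Simulation of a two-way absolute-agreement ICC: the same three operators scan all 40 patients, true ICC 0.80, 40,000 runs. The central 95% of estimates is 0.68-0.87 with no operator variance, 0.65-0.89 when operators account for 5% of total variance, and 0.59-0.91 when they account for 10%.

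**6. Single readings or the mean of three.** Take total variance 1, patient variance 0.80 and no systematic operator variance. The inter-observer ICC on means of three is then 0.80/[0.80 + (intra − 0.80) + (1 − intra)/3], where intra is the intra-observer ICC. A single-reading value of 0.80 becomes 0.83, 0.86 or 0.92 if intra is 0.95, 0.90 or 0.80.

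**The case against.** The strongest defence is that this is a pilot, labelled so in the study summary ("DESIGN Feasibility/Pilot Study") and in Section 3. A pilot may set its size pragmatically, and 40 exceeds the calculated 31. The first part stands: no power calculation was obligatory. But Section 7 does not use that argument; it presents a formal precision calculation. Exceeding a number computed for another parameter is no evidence about these outcomes, and the documents do not explain the step from 31 to 40.

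Two stronger readings are tempting, and the documents support neither:

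- A reader might infer that 40 patients are too few. Without a diameter SD, a target difference or a target ICC, adequacy cannot be judged either way.
- A reader might infer that the fixed 20/20 split rules out any prevalence estimate. It biases a crude one, but a weighted estimate would be possible if the referral mix were known. The point does not need this argument.

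Three cautions about the replacement figures also stand:

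- The group figures are for an unadjusted comparison, whereas an ANCOVA is planned. With balanced covariates and an assumed correlation of 0.5 with diameter, the factor is √(1−0.25) = 0.866, so 0.64 and 0.91 SD become about 0.55 and 0.79 SD. Section 7 names no covariates, so this gain cannot be counted on.
- ICC intervals that assume no systematic operator difference may flatter the study, because Sections 1.1 and 1.2 themselves stress how much ultrasound depends on the operator. Section 3 does not say whether the same three scientists scan every patient.
- Section 1.1 says that the depth of the iliac veins has limited ultrasound, so fewer than 40 patients may be evaluable.

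**Conclusion.** The point holds and should be fixed. The sample-size justification is wrong as written: the arithmetic is sound, but it answers a question that the study does not ask. Nothing in Section 7 conveys the precision of the posture change, the group difference or the ICCs. On standard assumptions, 40 patients give moderate precision for the posture change, 80% power only for a large group difference (about 0.91 SD unadjusted), and ICC intervals that run from fairly wide at 0.70 to narrow at 0.90. These figures assume approximate normality, the stated number of evaluable patients and ICC values that are not in the documents. The inter-observer intervals also assume no systematic operator difference. The error lies in the stated reason for the size; the size itself is not shown to be wrong.

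**What to change.** In Section 7:

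- Delete the prevalence calculation. Do not rely on the earlier study of 36 as justification.
- State 40 (20+20) as the single target, matching Section 3, and say that it was chosen pragmatically for a pilot if that is the reason.
- Give the precision from step 4 for the posture change, the group difference before covariate gain, and the ICCs, at 40 and at 31 evaluable patients. Label the ICC values as assumptions.
- State that the inter-observer intervals assume no systematic operator difference. Show beside them that estimates of an ICC of 0.80 would spread over about 0.59-0.91 if the same three operators scan every patient and operator differences are 10% of total variance.
- State whether the inter-observer ICC uses single readings or the mean of three.

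The cost is a rewritten paragraph in Section 7 and one cross-reference in Section 3, with no extra patients or procedures. The downside is a less favourable precision statement that is conditional on assumptions and, for the differences, expressed in SD units rather than millimetres.
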